		Administrative	8 (Research methods)	
Updated to reflect availability of data from Sweden until 2016, so this is now in line with other countries in the study.
 
Clarification of patient population as treatment naïve.
 
Clarification of exclusion criteria look back periods (5 years for mitral stenosis or mechanical heart valves; 9 months for pregnancy).
 
Definition of primary and secondary endpoints clarified to reflect updates in section 7.
 
Additional subgroup analyses added and clarified.
 
Additional section in 8 added for Record retention.
 
Definition of cumulative incidence updated to incorporate data over full follow up period.
	
Changes made to be consistent with greater data availability in Sweden , provide clarification on definition of patients as treatment naïve and clarify exclusion criteria. Endpoints updated to reflect clarified definitions in other sections.
 
Further subgroup analyses added after discussion with steering committee.
 
Additional sub-sections in section 8 added as required by Pfizer Clinical and Medical Controlled Document (CMCD) communication on the Global Standard Operating Procedure (GSOP) Clinical Trial 24 (CT24-GSOP) protocol and informed consent document templates 25-JUN-2018, as required by the General Data Protection Regulation.

ELIQUIS® (apixaban)
 B0661103 NON-INTERVENTIONAL STUDY PROTOCOL
 Amended, 05 JULY, 2018

				
Definition of on treatment definition for VKA updated to reflect comments from steering committee and to be consistent with BEYOND Norway, exploratory analyses performed using alternative method based on algorithm based on Danish data.
 
Sensitivity analyses added and clarified.
	
Cumulative incidence definition, calculation of VKA exposure and clarification of sensitivity analyses and addition of sensitivity analysis using regression adjustment using Cox regression were updated to reflect comments from real world data review committee and steering committees.

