8.5. Study size

Table 2 shows the number of users of NOACs in Denmark, Norway and Sweden in 2013-2015. Population risk of major bleeding in the study population is 2-3% per year (47). The number of eligible OAC users with NVAF will be smaller. A recent Danish comparative effectiveness study of OACs in new users with NVAF based on OACs use data between 2012 and 2015 enrolled approximately 35,000 initiators of warfarin, 12,000 initiators of dabigatran (150 mg); 7,000 initiators of rivaroxaban (20 mg), and 6,000 initiators of apixaban (5 mg) (13). In the apixaban group there were 90 cases of major bleeding after 1 year of follow-up and 109 cases after 2.5 years of follow-up (13). Another Danish study included more than 50,000 NOAC initiators with NVAF in August 2011-February 2016, of whom 70% were VKA naïve; the study included more than 12,000 initiators each of apixaban and rivaroxaban and more than 25,000 initiators of dabigatran. The study also demonstrated that about half of the NOAC initiators use these medications for the AF indication (19). In Norway, a study of anticoagulant-naïve NVAF patients initiating warfarin or NOACs in 2013-mid 2015, there were more than 6,000 initiators each of apixaban and rivaroxaban and nearly 8,000 initiators of dabigatran (16). Conservatively assuming the size of the apixaban cohort to be 24,000 patients in 2015, the expected number of major bleeding events in the apixaban group (the smallest) is 300 – 400 in the first year of follow-up.

Table 2. Persons ages 20 years or older with a dispensing of NOACs and VKAs for any indication in Denmark, Norway and Sweden, 2013-2015*

ATC code (active substance)	Denmark			Norway			Sweden		
	2013	2014	2015	2013	2014	2015	2013	2014	2015

B01AE07 (Dabigatran etexilate)	21,617	23,465	21,212	13,873	15,351	13,835	10,658	13,627	14,013
B01AF01 (Rivaroxaban)	10,877	16,023	22,500	13,394	20,759	25,439	9,652	21,140	33,868
B01AF02 (Apixaban)	1,772	8,023	17,926	2,258	8,636	21,498	2,072	17,132	46,926
B01AA(VKAs)**	91,202	89,783	87,851	87,900	77,681	69,212	202,729	202,729	188,966

*Unique in each calendar year; age categories as reported by the sources listed below
 **Nearly all warfarin, e.g., in 2015 Denmark 98.2%, Norway 99.9%;Sweden 99.8%
 Sources:
 Denmark www.medstat.dk;
 Norway www.norpd.no;
 Sweden <http://www.socialstyrelsen.se/statistik/statistikdatabas/lakemedel%>

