8.7.2. Main analysis

To compare risks of the endpoints across the study cohorts, time to event analysis will be undertaken, using Cox proportional-hazards regression, with death as competing risk for endpoints not including death. Crude and adjusted HRs and 95% confidence intervals (CI) will be estimated for initiators of each NOAC. Follow-up will end on the date of a given endpoint, date of death (for non-death endpoints), date of discontinuation of or switch from the index OAC, date of emigration, or 31 December 2016, whichever comes first. A patient will be considered on-treatment from the date of the first dispensing of the index OAC and for the subsequent number of days corresponding to the number of tablets in all dispensed packages for rivaroxaban (used once daily) or half the number of tablets in all dispensed packages for dabigatran or apixaban (used twice daily) as long as there are no more than 30 days between the expiration and the start of the two adjacent dispensings. A discontinuation will be recorded as soon as 31 days elapse after the expiration of the number of days in a given dispensing (date of dispensing + days supplied + 31 days) in the absence of the next dispensing of the same OAC.

The approach to calculate the warfarin discontinuation date will be based on the median daily dose for all warfarin patients; this median daily dose will be used to calculate an end of supply date based on the dispensing strength and number of tablets in a package for each patient. Discontinuation will be assumed if there was no warfarin prescription within 30 days of the end date of the supply.

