8.7.3. Sensitivity analysis

The following sensitivity analyses will be performed overall, for the primary endpoints and the composite secondary endpoint:

1. The intention-to-treat (ITT) like analyses: the overall comparative PS-matched analyses of the primary endpoints and the composite secondary endpoint will be repeated whereby patients in each OAC cohort will be followed from the index date until a given endpoint, death, emigration, or study end (no censoring by discontinuation or switching)
2. The overall comparative analyses of the primary endpoints and the composite secondary endpoint in the propensity score (PS)-matched analysis set will be repeated whereby the on-treatment time for patients treated with warfarin will be estimated based on a recently published methods using on maximum likelihood estimation of a parametric two-component mixture model for the waiting time distribution (52, 53). The algorithm found that 80% of current warfarin users will have presented themselves again for a refill after 91 days. A 30-day grace period will be added at the end of the 91 days
3. The overall comparative analyses of the primary endpoints and the composite secondary endpoint will be repeated in the full analysis dataset using conventional adjustment instead of PS matching
4. The overall comparative analyses of the primary endpoints and the composite secondary endpoint will be repeated in the full analysis dataset using conventional adjustment instead of PS matching
5. Analysis stratified on the initial dose will be performed after PS rematching within the initial dose defined strata.

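### Sensitivity analysis 2 applies one Danish-derived 91-day refill time to all three countries, which weakens its check of the warfarin exposure rule in Norway and Sweden

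*Protocol*

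**What the plan says.** The main warfarin rule is in section 8.7.2: "The approach to calculate the warfarin discontinuation date will be based on the median daily dose for all warfarin patients". That dose is combined with the strength and tablet count of each dispensing to give an end-of-supply date. A 30-day allowance follows: "Discontinuation will be assumed if there was no warfarin prescription within 30 days of the end date of the supply".

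Section 8.7.3, item 2, repeats the propensity-score-matched comparisons with warfarin time taken instead from a parametric waiting-time-distribution method. It fixes the result as a number: "The algorithm found that 80% of current warfarin users will have presented themselves again for a refill after 91 days". It then says: "A 30-day grace period will be added at the end of the 91 days". As written, the value depends neither on country nor on the quantity dispensed.

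The source of the figure appears only in the amendment table in section 4, which describes "exploratory analyses performed using alternative method based on algorithm based on Danish data".

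On scope, section 8.7.3 opens with "The following sensitivity analyses will be performed overall, for the primary endpoints and the composite secondary endpoint", while section 8.7 says that all analyses are run both on the combined data and by country.

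**The concern.** A refill-time percentile summarises how much is dispensed at a time and how often patients return. It describes a dispensing system as well as a drug, so a value estimated in one country needs some support before it is used in another. The protocol gives none. Section 6 refers to similar clinical practice and section 8.4 to similar data structure and coding, but neither mentions package sizes or refill intervals.

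In item 2, NOAC time is still counted from tablets, so any misfit falls on warfarin, the comparator in every contrast. If refill intervals in Norway or Sweden are longer than the Danish value implies, continuing warfarin users there are cut off early. If they are shorter, patients who have stopped are counted as treated for longer. What is at stake is how item 2 can be interpreted; the primary hazard ratios do not use this rule.

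**Working it through.** **1. How much of the warfarin experience lies outside Denmark.** The inputs are the VKA row of Table 2 (section 8.5), in the order Denmark, Norway, Sweden. The share outside Denmark is (Norway + Sweden) / total.

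- 2013: (87,900 + 202,729) / (91,202 + 87,900 + 202,729) = 290,629 / 381,831 = 76.1%
- 2014: (77,681 + 202,729) / (89,783 + 77,681 + 202,729) = 280,410 / 370,193 = 75.7%
- 2015: (69,212 + 188,966) / (87,851 + 69,212 + 188,966) = 258,178 / 346,029 = 74.6%

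Applying the 2015 warfarin percentages in the table footnote (98.2%, 99.9%, 99.8%) gives 86,270, 69,143 and 188,588 users, and a share of 74.9%.

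Two cautions apply. The table covers "Persons ages 20 years or older with a dispensing of NOACs and VKAs for any indication in Denmark, Norway and Sweden", so it shows prevalent use, not new users with non-valvular AF. The Swedish counts for 2013 and 2014 are identical, which may be a copying slip; the 2015 figure does not depend on them.

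**2. The 91 days.** This cannot be reproduced, because the protocol gives no refill data or model parameters. The allowance per dispensing is 91 + 30 = 121 days.

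**3. What a misfit could do (illustration only).** Assume that refill gaps among continuing users are lognormal with log-SD s between 0.4 and 0.8. Neither the distribution nor the range comes from the protocol. If P is a country's 80th percentile, the share of gaps above 121 days is 1 − Φ( ln(121/P)/s + 0.8416 ), where 0.8416 is the 80th percentile of the standard normal.

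For P = 91, ln(121/91) = 0.2849:

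- s = 0.4: 1 − Φ(0.712 + 0.842) = 6.0%
- s = 0.8: 1 − Φ(0.356 + 0.842) = 11.6%

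The same formula for other values of P, as the range over s from 0.4 to 0.8:

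- P = 70 days: 1.4% to 6.4%
- P = 110 days: 14.0% to 16.8%
- P = 121 days: 20% by definition
- P = 150 days: 28.3% to 38.0%

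So some continuing users are read as stopped even where 91 days is right. The cost of carrying the value across borders is the difference from that 6.0% to 11.6%, and it can go either way.

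**4. What item 2 still tests.** The main rule uses dose, strength and tablet count plus 30 days; item 2 uses a fixed 121 days. These are structurally different, so the comparison does show whether the hazard ratios move when warfarin time is assigned in another way.

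**The case against.** The strongest reply is that a sensitivity analysis need not be a gold standard, and that the results have other protection. The intention-to-treat-like analysis in item 1 of section 8.7.3 uses no discontinuation date and cannot be affected by a refill time. Section 8.7 promises country-stratified results, and the word overall in section 8.7.3 may only mean outside the subgroups. Section 8.9 already lists misclassification of treatment timing as a limitation, the amendment table calls this analysis exploratory, and the SAP, which is not at hand, may refine it.

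Most of this stands, and it rules out three stronger readings that a reader might infer.

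- *That item 2 cannot test the warfarin rule at all.* It can, because the two rules differ in kind, and it stays interpretable for Denmark.
- *That warfarin users in Norway and Sweden would be wrongly censored on a large scale.* Nothing in the protocol shows that refill intervals differ between the countries.
- *That about half of adherent users would be falsely stopped within three refill cycles.* That figure is 1 − (1 − 0.20)³ = 48.8%. It needs 20% of users still without a refill at day 121, whereas the protocol gives 20% at day 91. In Denmark it would mean that nobody refills during the grace period; elsewhere it would need an 80th percentile of 121 days, which the protocol does not report. It also treats cycles as independent. If long gaps recur in the same patients, the cumulative figure is lower.

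The reply does not remove the point. The intention-to-treat-like analysis drops discontinuation altogether and so answers a different question. Stratifying by country would still apply the Danish value in Norway and Sweden. The protocol itself writes in the 91 days, so the value is a stated choice and not a detail left to the SAP.

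**Conclusion.** The point holds as a weakness of one sensitivity analysis. Item 2 is the only alternative on-treatment definition for warfarin, and its one fixed value is tied by the protocol to Danish data. By the proxy in Table 2, about 75% of VKA use lies in the other two countries, and no section justifies the transfer. For Norway and Sweden, a difference from the main result could reflect a poorly fitting refill time, and agreement does not show that the main rule is sound there.

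The size and direction of any error are unknown. The lognormal figures show only that the effect could be small or appreciable, depending on refill distributions that the protocol does not give. The country mix of new users with non-valvular AF may differ from Table 2. The primary hazard ratios are unaffected.

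**What to change.** In section 8.7.3, item 2, replace the single value. Estimate the 80th-percentile refill time separately from the Danish, Norwegian and Swedish warfarin dispensings with the waiting-time method already named, and apply each country's value plus the existing 30-day grace period. Report item 2 by country as well as overall, and align the opening sentence of section 8.7.3 with section 8.7 so that this is explicit. State in item 2 where any fixed value comes from.

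If country-specific estimation is not feasible, state the Danish origin of the 91 days and repeat item 2 over a pre-specified range of refill times.

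The cost is a little more analysis work on dispensings that the drug file of the common data model (section 8.6) is planned to hold. No new data are needed and the main analysis stays as it is.

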8.8. Quality control

Data management and analyses will be conducted according to each institution's standard procedures. At a minimum, all study documents (protocol, report, publications) will be reviewed by the entire research team, and a senior epidemiologist in each institution will review the report before submission to the sponsor. Clinical expertise is available for appropriate interpretation of results. At the start of the project, a kick-off meeting will establish a regular communication plan (via e-mail and regular teleconferences); and establish internal timelines to be completed in time to allow review and quality control before submitting each deliverable.

Each institution will follow its internal quality control procedures and will ensure the necessary compliance with local data protection, storage and archiving, and patient privacy laws and regulations and will obtain all permission necessary to conduct this study.

8.9. Strengths and limitations of the research methods

All Scandinavian countries have tax-supported universal health care; routine recording of prescription dispensings, hospital diagnoses, migrations and deaths, and the possibility for individual-level data linkage of all data, thus enabling nearly complete follow-up of the entire populations and virtually no selection bias in epidemiologic studies.

Data in Scandinavian national registries have been validated and the validity has in general been found to be high in all countries (54-62). For example, the positive predictive value of the combined diagnosis of AF and/or atrial/flutter and other cardiovascular diagnoses in the Danish National Patient registry typically exceeds 95% (63-65), and similar findings have been reported from Norway (51) and in Sweden (66). Other hospital diagnoses have also been validated, including the Charlson Comorbidity Index (39, 42). For drugs used chronically, there is also high level of agreement between general practitioner and dispensing records (67). Furthermore, the CHA₂DS₂VASc, CHADS₂ and the HAS-BLED scores can be constructed based on registry data (the HAS-BLED version does not include data on labile INR) (68, 69).

Limitations of the methods include misclassification of treatment presence and timing by relying on dispensing information, and potential confounding by indication, whereby an OAC choice is guided by patients' characteristics that predict bleeding outcomes. Using 12 months OAC-free pre-index date period to identify new users may include patients with previous exposure to OACs; thus not all OAC initiators in this study will be truly treatment naive. Furthermore, the definition of the endpoint 'major bleeding' in this study that relies on routinely collected data, will be inherently different from the definition of the 'major bleeding' endpoint used in RCTs. There is a risk of under-ascertainment of absolute risks of bleeding outcomes if not all of them are reflected/correctly recorded by hospital diagnoses. At the same time, specificity of recording is high and relative estimates are therefore expected to be unbiased. Finally, routinely collected data contain no information on the quality of warfarin treatment control or dose. Nor can severity of most comorbidities be established.

8.10. Other aspects

Not applicable.

9. PROTECTION OF HUMAN SUBJECTS

9.1. Patient information

This analysis dataset involves data that exist in anonymized structured format and contain no patient personal information.

9.2. Patient Consent

As this study involves anonymized structured or unstructured data, which according to applicable legal requirements do not contain data subject to privacy laws, obtaining informed consent from patients by Pfizer is not required.

9.3. Patient withdrawal

Not applicable.

9.4. Institutional Review Board (IRB)/Independent Ethics Committee (IEC)

Approval by an IRB is not required for studies based on routinely collected data. All investigators will follow appropriate local procedures to comply with all applicable local laws and regulation. All relevant documentation will be kept on file. Ethical conduct of the study

The study will be conducted in accordance with legal and regulatory requirements, as well as with scientific purpose, value and rigor and follow generally accepted research practices described in Guidelines for Good Pharmacoepidemiology Practices (GPP) issued by the International Society for Pharmacoepidemiology (ISPE), European Medicines Agency (EMA) Guideline for Good Pharmacovigilance Practice (GVP).

10. MANAGEMENT AND REPORTING OF ADVERSE EVENTS/ADVERSE REACTIONS

This study includes unstructured data (e.g., narrative fields in the database) that will be converted to structured (i.e., coded) data solely by a computer using automated/algorithmic methods and/or data that already exist as structured data in an electronic database. In these data sources, it is not possible to link (i.e., identify a potential association between) a particular product and medical event for any individual. Thus, the minimum criteria for reporting an adverse event (i.e., identifiable patient, identifiable reporter, a suspect product, and event) are not available and AEs are not reportable as individual AE reports.

11. PLANS FOR DISSEMINATING AND COMMUNICATING STUDY RESULTS

At the end of this study a single report based on analysis of combined data from the three countries (and country-specific results) will be prepared and submitted to the MAH. The investigators maintain the rights to present results from this study at scientific conferences and to publish the results in peer-reviewed journals.

COMMUNICATION OF ISSUES

In the event of any prohibition or restriction imposed (e.g., clinical hold) by an applicable Competent Authority in any area of the world, or if the investigator is aware of any new information which might influence the evaluation of the benefits and risks of a Pfizer product, Pfizer should be informed immediately. In addition, the investigator will inform Pfizer immediately of any serious breaches of this non-interventional study protocol that the investigator becomes aware of.

ANNEX 2. ENCEPP CHECKLIST FOR STUDY PROTOCOLS

**Study title: BEYOND Pooled –
 Part of the BEYOND study program (BENefit of NOACs studY of nOn-valvular AF patieNts in NorDic countries)**

Study reference number:
 EUPAS21192

Section 1: Milestones	Yes	No	N/A	Section Number
1.1 Does the protocol specify timelines for				
1.1.1 Start of data collection ¹				5
1.1.2 End of data collection ²				5
1.1.3 Study progress report(s)				
1.1.4 Interim progress report(s)				
1.1.5 Registration in the EU PAS register				5
1.1.6 Final report of study results.				5

Comments:

Milestones are contingent on data delivery from the data custodians

Section 2: Research question	Yes	No	N/A	Section Number
2.1 Does the formulation of the research question and objectives clearly explain:				
2.1.1 Why the study is conducted? (e.g. to address an important public health concern, a risk identified in the risk management plan, an emerging safety issue)				6
2.1.2 The objective(s) of the study?				7
2.1.3 The target population? (i.e. population or subgroup to whom the study results are intended to be generalised)				7
2.1.4 Which hypothesis(-es) is (are) to be tested?				
2.1.5 If applicable, that there is no a priori hypothesis?				

Comments:

¹ Date from which information on the first study is first recorded in the study dataset or, in the case of secondary use of data, the date from which data extraction starts.

² Date from which the analytical dataset is completely available.

Section 3: Study design		Yes	No	N/A	Section Number
3.1	Is the study design described? (e.g. cohort, case-control, cross-sectional, new or alternative design)				8.1
3.2	Does the protocol specify whether the study is based on primary, secondary or combined data collection?				8.1 and 8.4
3.3	Does the protocol specify measures of occurrence? (e.g. incidence rate, absolute risk)				8.7.1
3.4	Does the protocol specify measure(s) of association? (e.g. relative risk, odds ratio, excess risk, incidence rate ratio, hazard ratio, number needed to harm (NNH) per year)				8.7.2
3.5	Does the protocol describe the approach for the collection and reporting of adverse events/adverse reactions? (e.g. adverse events that will not be collected in case of primary data collection)				10

Comments:

--

Section 4: Source and study populations		Yes	No	N/A	Section Number
4.1	Is the source population described?				8.2
4.2	Is the planned study population defined in terms of:				
	4.2.1 Study time period?				8.2
	4.2.2 Age and sex?				8.2
	4.2.3 Country of origin?				8.2
	4.2.4 Disease/indication?				8.2
	4.2.5 Duration of follow-up?				8.1
4.3	Does the protocol define how the study population will be sampled from the source population? (e.g. event or inclusion/exclusion criteria)				8.2

Comments:

--

Section 5: Exposure definition and measurement		Yes	No	N/A	Section Number
5.1	Does the protocol describe how the study exposure is defined and measured? (e.g. operational details for defining and categorising exposure, measurement of dose and duration of drug exposure)				8.3.1
5.2	Does the protocol address the validity of the exposure measurement? (e.g. precision, accuracy, use of validation sub-study)				8.9
5.3	Is exposure classified according to time windows? (e.g. current user, former user, non-use)				
5.4	Is exposure classified based on biological mechanism of action and taking into account the pharmacokinetics and pharmacodynamics of the drug?				8.7.2

Comments:

Re 5.3: On-treatment and overall risks will be estimated
--

Section 6: Outcome definition and measurement		Yes	No	N/A	Section Number
6.1	Does the protocol specify the primary and secondary (if applicable) outcome(s) to be investigated?				8.3.2
6.2	Does the protocol describe how the outcomes are defined and measured?				8.3.2
6.3	Does the protocol address the validity of outcome measurement? (e.g. precision, accuracy, sensitivity, specificity, positive predictive value, prospective or retrospective ascertainment, use of validation sub-study)				8.9
6.4	Does the protocol describe specific endpoints relevant for Health Technology Assessment? (e.g. HRQoL, QALYs, DALYS, health care services utilisation, burden of disease, disease management)				8.3.2.3

Comments:

--

Section 7: Bias		Yes	No	N/A	Section Number
7.1	Does the protocol describe how confounding will be addressed in the study?				8.7
	7.1.1. Does the protocol address confounding by indication if applicable?				8.7
7.2	Does the protocol address:				
	7.2.1. Selection biases (e.g. healthy user bias)				8.9
	7.2.2. Information biases (e.g. misclassification of exposure and endpoints, time-related bias)				8.9
7.3	Does the protocol address the validity of the study covariates?				8.9

Comments:

--

Section 8: Effect modification		Yes	No	N/A	Section Number
8.1	Does the protocol address effect modifiers? (e.g. collection of data on known effect modifiers, sub-group analyses, anticipated direction of effect)				8.3.3 and 8.3.4

Comments:

Re 8.1: subgroup analyses are planned

Section 9: Data sources		Yes	No	N/A	Section Number
9.1	Does the protocol describe the data source(s) used in the study for the ascertainment of:				
	9.1.1 Exposure? (e.g. pharmacy dispensing, general practice prescribing, claims data, self-report, face-to-face interview)				8.4

Section 9: Data sources		Yes	No	N/A	Section Number
9.1.2	Outcomes? (e.g. clinical records, laboratory markers or values, claims data, self-report, patient interview including scales and questionnaires, vital statistics)				8.4
9.1.3	Covariates?				8.5
9.2	Does the protocol describe the information available from the data source(s) on:				
9.2.1	Exposure? (e.g. date of dispensing, drug quantity, dose, number of days of supply prescription, daily dosage, prescriber)				8.4
9.2.2	Outcomes? (e.g. date of occurrence, multiple event, severity measures related to event)				8.4
9.2.3	Covariates? (e.g. age, sex, clinical and drug use history, co-morbidity, co-medications, lifestyle)				8.4
9.3	Is a coding system described for:				
9.3.1	Exposure? (e.g. WHO Drug Dictionary, Anatomical Therapeutic Chemical (ATC) Classification System)				SAP Appendix 1
9.3.2	Outcomes? (e.g. International Classification of Diseases (ICD)-10, Medical Dictionary for Regulatory Activities (MedDRA))				SAP Appendix 1
9.3.3	Covariates?				SAP Appendix 1
9.4	Is a linkage method between data sources described? (e.g. based on a unique identifier or other)				8.4

Comments:

--

Section 10: Analysis plan		Yes	No	N/A	Section Number
10.1	Is the choice of statistical techniques described?				8.7 and SAP section 8
10.2	Are descriptive analyses included?				8.7 and SAP section 8
10.3	Are stratified analyses included?				8.7 and SAP section 8
10.4	Does the plan describe methods for adjusting for confounding?				8.7 and SAP section 8
10.5	Does the plan describe methods for handling missing data?				
10.6	Is sample size and/or statistical power estimated?				8.5

Comments:

--

Section 11: Data management and quality control		Yes	No	N/A	Section Number
11.1	Does the protocol provide information on data storage? (e.g. software and IT environment, database maintenance and anti-fraud protection, archiving)				8.6

Section 11: Data management and quality control	Yes	No	N/A	Section Number
11.2 Are methods of quality assurance described?				8.8
11.3 Is there a system in place for independent review of study results?				11

Comments:

Re 11.3: There is an independent Steering Committee + publication plan

Section 12: Limitations	Yes	No	N/A	Section Number
12.1 Does the protocol discuss the impact on the study results of:				
12.1.1 Selection bias?				8.9
12.1.2 Information bias?				8.9
12.1.3 Residual/unmeasured confounding? (e.g. anticipated direction and magnitude of such biases, validation sub-study, use of validation and external data, analytical methods)				8.9
12.2 Does the protocol discuss study feasibility? (e.g. study size, anticipated exposure, duration of follow-up in a cohort study, patient recruitment)				8.5

Comments:

Section 13: Ethical issues	Yes	No	N/A	Section Number
13.1 Have requirements of Ethics Committee/ Institutional Review Board been described?				9
13.2 Has any outcome of an ethical review procedure been addressed?				9
13.3 Have data protection requirements been described?				9

Comments:

Section 14: Amendments and deviations	Yes	No	N/A	Section Number
14.1 Does the protocol include a section to document amendments and deviations?				4

Comments:

Section 15: Plans for communication of study results	Yes	No	N/A	Section Number
15.1 Are plans described for communicating study results (e.g. to regulatory authorities)?				
15.2 Are plans described for disseminating study results externally, including publication?				11

Comments:

Re 15.1: not a regulator-mandated PASS

Name of the main authors of the protocol: [name], DSc
[name] [name], PhD

Date: 27/September/2017

Signature: _____
